## 7.4.4 Supplementary analysis

As a supplementary analysis, the joint BLRM may be analyzed using DLT data from the whole on-treatment period instead of DLT data from the MTD evaluation period. This analysis will include all treated patients, including 'backfill' patients and cross-over patients.

#### 7.5 SECONDARY OBJECTIVE ANALYSIS

## 7.5.1 Key secondary objective analysis

This section is not applicable as no key secondary endpoint has been specified in the protocol.

## 7.5.1.1 Main analysis

This section is not applicable as no key secondary endpoint has been specified in the protocol.

## 7.5.1.4 Supplementary analysis

Date: 8 Apr 2024, Version 1.0

This section is not applicable as no key secondary endpoint has been specified in the protocol.

## 7.5.2 Secondary objective analysis

## OR based on RECIST 1.1: (CTP version 1 and 2)

Objective response (OR) by RECIST 1.1 will be presented in terms of objective response rate (ORR), which is defined as the rate of patients whose best overall response is confirmed CR or PR as determined by the Investigator's assessment according to RECIST 1.1 from date of first treatment administration until the earliest of disease progression, death or last evaluable tumor assessment before start of subsequent anti-cancer therapy, loss to follow-up or withdrawal of consent.

## OR based on itRECIST: (CTP version 3 and later)

Objective response (OR) by itRECIST will be presented in terms of objective response rate (ORR), which is defined as the rate of patients whose best overall response is confirmed itCR or itPR as determined by the Investigator's assessment according to itRECIST from date of first treatment administration until the earliest of confirmed disease progression, death or last evaluable tumor assessment before start of subsequent anti-cancer therapy, loss to follow-up or withdrawal of consent.

Each patient treated under CTP version 1 or 2 will be assigned to one of the following best overall response categories according to RECIST 1.1: CR, PR, stable disease (SD), progressive disease (PD), not evaluable (NE).

Proprietary confidential information © 2024 Boehringer Ingelheim International GmbH or one or more of its affiliated companies.

Each patient treated under CTP version 3 or later will be assigned to one of the following best overall response categories according to itRECIST: intratumoral CR, intratumoral PR, intratumoral SD, intratumoral unconfirmed PD, intratumoral confirmed PD, not evaluable (NE).

A best overall response of CR and PR (RECIST 1.1) or intratumoral CR and intratumoral PR (itRECIST) must be confirmed by a subsequent tumor assessment, i.e. a confirmed response requires a repeated observation on two occasions at least 4 weeks apart.

For a best overall response of SD (RESIST 1.1) or intratumoral SD (itRECIST), a minimal duration of 35 days (6 weeks +/-1 week to account for the imaging time window) is required.

ORR according to RECIST v1.1 and ORR according to itRECIST will be summarized descriptively with 95% confidence intervals using the Wilson method. Patients' time to tumor response and duration of response will be visualized by swimmer plots.

Best percentage change from baseline in size of target lesions (CTP version 1 and 2) and Best percentage change from baseline in size of non-injected target lesions (CTP version 3 and later) will be analyzed using descriptive statistics as well as waterfall plots. All lesion measurements recorded from start of trial treatment until the earliest of progression (confirmed intratumoral PD with CTP version 3 and later), start of subsequent anti-cancer therapy, loss to follow-up or withdrawal of consent will be taken into account when calculating the best percentage change from baseline.

Similarly, Best percentage change from baseline in size of injected lesions (CTP version 1 and 2) and Best percentage change from baseline in size of injected target lesions (CTP version 3 and later) will be analyzed using descriptive statistics as well as waterfall plots. All lesion measurements recorded from start of trial treatment until the earliest of progression (confirmed intratumoral PD with CTP version 3 and later), start of subsequent anti-cancer therapy, loss-to follow-up or withdrawal of consent will be taken into account when calculating the best percentage change from baseline.

However, for the last two endpoints, special attention should be paid to the derivation of baseline, which will be determined according to the itRECIST publication: For each injected (target) lesion, the baseline is its diameter just before it is first injected, and the baseline SOD for injected lesions is the sum of these diameters, which may originate from different time points. The best response SOD is the SOD of these lesions at each lesion's smallest size after injection, again, possibly at different time points.

All secondary endpoints will be presented dose cohort, separately for Arm A and Arm B.

Proprietary confidential information © 2024 Boehringer Ingelheim International GmbH or one or more of its affiliated companies.

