10.3 TUMOUR ASSESSMENTS

Tumour assessments will be performed according to Response criteria for intratumoural immunotherapy in solid tumours (itRECIST) ([R20-2734](#)).

At baseline, tumour lesions and lymph nodes will first be categorised as measurable or non-measurable. Measurable lesions are then classified as target (selected to be observed quantitatively) or non-target (selected to be observed qualitatively), and the decision about which lesion is to be injected is made. In this trial, a lesion selected for injection must be measurable (see [Section 10.3.1](#) for details).

At baseline, one lesion projected for injection should be classified as target injected (T-I), only in exceptional cases, two lesions may be projected for injection and thus be classified as T-I (refer to [Section 4.1.4.1](#)). Up to 5 lesions can be classified as target non-injected (T-NI). All lesions not chosen as target are observed qualitatively as non-target. See [Figure 10.3: 1](#) for details on the classifications of lesions at baseline. As in this trial, a lesion selected for injection must be measurable, lesions selected for injection at baseline can only be target (refer to [Section 4.1.4.1](#)).

[figure not shown]

Figure 10.3: 1 Classification of lesions at baseline

Lesions designated as T-I will be used to evaluate the injected lesion response. Lesions designated as T-NI should remain non-injected for as long as possible to allow assessment of the maximal non-injected lesion response. However, in the case that there is no other lesion available for injection, or the T-NI lesions are enlarging, T-NI lesions may be injected and recategorized to T-I, if they meet the criteria for injection.

Similarly to T-NI lesions, also NT-NI lesions may be injected and recategorized to NT-I, if they meet the criteria for injection (in particular if they are measurable according to [Section 10.3.1](#)). However, even though measurable, these lesions will contribute to the overall response only with their qualitative assessment.

A sum of diameters (SOD; longest diameters for extranodal lesions and short axis for lymph nodes) will be calculated for all target lesions combined and separately for T-I and T-NI-lesions.

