## 6.7 BASELINE, TIME WINDOWS AND CALCULATED VISITS

Unless otherwise specified baseline is defined as the time point closest to but prior to the first administration of any study medication. If no time is specified and the date is the same as the first administration date, then it will still be considered baseline if not specified otherwise. If there is no measurement earlier than the first administration of study medication, then no baseline will be derived.

For the analysis of 'Best percentage change from baseline in size of injected lesions' (CTP version 1 and 2) and 'Best percentage change from baseline in size of injected target lesions' (CTP version 3 and later) the derivation of baseline will follow the itRECIST publication, details are given in Section 7.5.2.

Study days and visits will be labelled according to the flowchart in the CTP.

Proprietary confidential information © 2024 Boehringer Ingelheim International GmbH or one or more of its affiliated companies.

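### The window for the non-injected target lesion endpoint does not stop when such a lesion is injected, so injection effects or a dropped lesion can appear as distant shrinkage

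*SAP*

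**What the plan says.** Protocol 10.3 sorts target lesions into injected (T-I) and non-injected (T-NI), with up to five T-NI lesions, and calculates a sum of diameters for each group. T-NI lesions are to be left alone for as long as possible. But if no other lesion is available, or if "the T-NI lesions are enlarging, T-NI lesions may be injected and recategorized to T-I, if they meet the criteria for injection". Protocol 10.3 bases the non-injected response on the sum for those lesions and refers to Section 7. Protocol 7.2.3 adds only that the endpoint gets descriptive statistics and waterfall plots.

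The SAP fixes two things for the non-injected endpoint (protocol version 3 and later):

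- **Baseline.** SAP 6.7 gives the default: "Unless otherwise specified baseline is defined as the time point closest to but prior to the first administration of any study medication". An exception exists, but only for the injected-lesion endpoints, where "CTP version 3 and later) the derivation of baseline will follow the itRECIST publication".
- **Window.** SAP 7.5.2 uses "All lesion measurements recorded from start of trial treatment until the earliest of progression (confirmed intratumoral PD with CTP version 3 and later", then lists subsequent anti-cancer therapy, loss to follow-up and withdrawal of consent. First injection of the lesion is not on the list.

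For the injected-lesion endpoints SAP 7.5.2 does deal with lesions that change status: "However, for the last two endpoints, special attention should be paid to the derivation of baseline", and then "For each injected (target) lesion, the baseline is its diameter just before it is first injected". No matching rule covers the T-NI sum that the lesion leaves.

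**The concern.** The SAP handles one side of the move only. A recategorised lesion gets a new baseline where it arrives, and nothing is said about where it came from. That leaves two ways to compute the T-NI change afterwards, and either can show shrinkage that did not occur in non-injected disease.

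- **Lesion kept in the T-NI sum.** This is the literal result of counting all measurements. Its response to direct injection enters the non-injected endpoint, and the same shrinkage also counts in the injected endpoint.
- **Lesion dropped from follow-up, its diameter left in the baseline sum.** The sum falls by construction.

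The endpoint takes the best value. Compared with stopping at first injection, extra time points under either route can lower the result or leave it unchanged, never raise it. Enlargement is one of the two stated grounds for injecting a T-NI lesion, so the affected patients are not a random subset. The window also runs to confirmed progression, and protocol 4.1.2.3 permits treatment after initial radiological progression under conditions. A growing T-NI lesion can therefore be injected while its measurements still count.

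This is a named secondary endpoint. Protocol 5.7 gives the contrast between injected and non-injected response as an aim of itRECIST. SAP 7.5.2 shows results by dose cohort, and protocol 3.1.2 intends at most 8 patients per dose level, so one affected patient can be 1 bar in 8.

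**Working it through.** The plan states no figure on this point, so there is none to reproduce. The check is direct arithmetic on the sum of diameters.

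**Inputs from the documents:** k = 1 to 5 T-NI lesions (protocol 10.3); fixed pre-treatment baseline (SAP 6.7); no stop at injection (SAP 7.5.2).

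**Assumptions, not in the documents:** k lesions of equal diameter D (20 mm in the runs, but D cancels); one grows by g = 20% and is then injected; the others do not change; the injected lesion shrinks by s = 30%, 50% or 100% of its pre-injection size. There is thus no distant shrinkage in any row.

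**Formulas:**

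- Last value before injection: [(k - 1) + 1.2]/k - 1 = 0.2/k
- Lesion kept: [(k - 1) + 1.2(1 - s)]/k - 1 = [1.2(1 - s) - 1]/k
- Lesion dropped from follow-up only: (k - 1)/k - 1 = -1/k

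| k | Last value before injection | Kept, s = 30% | Kept, s = 50% | Kept, s = 100% | Dropped from follow-up only |
|---|---|---|---|---|---|
| 1 | +20.0% | -16.0% | -40.0% | -100.0% | -100.0% |
| 2 | +10.0% | -8.0% | -20.0% | -50.0% | -50.0% |
| 3 | +6.7% | -5.3% | -13.3% | -33.3% | -33.3% |
| 4 | +5.0% | -4.0% | -10.0% | -25.0% | -25.0% |
| 5 | +4.0% | -3.2% | -8.0% | -20.0% | -20.0% |

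With k = 1 the dropped sum is empty, and in practice might be set to missing.

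**When the kept-lesion effect appears.** The apparent change is negative only if 1.2(1 - s) < 1, that is, s > 1 - 1/1.2 = 16.7%. With less local shrinkage the lesion is still at or above its pre-treatment size and no false shrinkage is shown.

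**Removing the lesion from both sums.** This is the obvious repair. In the table's setting it gives 0% for k of 2 or more and no value for k = 1. It is not neutral when the other lesions are shrinking. Take lesions of 30, 25 and 20 mm that become 36, 20 and 16 mm. Just before injection of the 36 mm lesion the change is 72/75 - 1 = -4%. With that lesion removed from both sums it is (20 + 16)/(25 + 20) - 1 = 36/45 - 1 = -20%, and a best-value rule would select the second figure.

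**The case against.** The strongest reply is that the protocol already implies the answer. Once injected, a T-NI lesion becomes T-I, the two sums are separate, and each response rests on its own lesions. Keeping the lesion would count it in both endpoints. Nor does any sentence tell a programmer to divide a reduced sum by the full baseline; a percentage change ordinarily has the same lesions above and below the line. This stands as far as it goes. A reader might infer that the SAP orders recategorised lesions to stay in the T-NI sum, or orders a mismatched baseline. The documents support neither. But the reply does not close the gap: the written window has no stop at injection, and no rule takes the lesion's diameter out of the baseline sum. The natural repair, dropping it from both sums, has its own bias.

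The itRECIST publication may settle the matter. It is not among the documents, and the SAP invokes it for baseline only for the injected-lesion endpoints. If it contains a rule, the SAP should state that rule for this endpoint too.

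A reader might also infer that the error always favours the drug, or that changes of -40% or more are typical. Neither is supported. The kept-lesion effect needs shrinkage below the pre-treatment size, and with 30% local shrinkage it is only -8.0% (k = 2) to -3.2% (k = 5).

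Exposure is also limited. T-NI lesions are to stay non-injected as long as possible, repeat doses go preferably into the same lesion, and only superficial lesions may be injected (protocol 4.1.4.1). The endpoint is secondary and descriptive, protocol 5.7 calls the evaluation of activity preliminary and exploratory, and SAP section 4 records that development has been terminated. All of this stands and limits the weight of the point.

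**Conclusion.** The point holds in a limited form. It is more than a missing detail, because the SAP states both a window and a baseline for this endpoint, and following them literally can produce a wrong value in a patient whose T-NI lesion is injected. It applies only to the version 3 and later endpoint and only to such patients, whose number the documents do not give.

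The size in an affected patient rests on the assumptions above (equal lesions, 20% growth before injection, the others stable). For k = 2 to 5, false shrinkage runs from 20% down to 8% if the lesion is kept with 50% local shrinkage, and from 50% down to 20% if it is dropped from follow-up only. The last values before injection were +10% to +4%. No MTD, error rate or sample size is touched. What is at risk is the reading of small-cohort waterfall plots as evidence of an effect beyond the injected lesion.

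**What to change.** Add a rule to SAP 7.5.2. Calculate the best percentage change in non-injected target lesions from T-NI sums up to and including the last assessment before the first injection of any T-NI lesion, against the baseline sum of the same lesions. Flag affected patients in the waterfall plot. The change in the remaining never-injected lesions against their own baseline may be shown as a supplementary display only, because removing an enlarging lesion can flatter it and it has no value when that lesion was the only one.

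The cost is a sentence or two in the SAP and a programming rule. The injected lesion is already captured in the eCRF for each injection (protocol 4.1.2.1.2), and administration dates are recorded (protocol 5.3). When lesions may be injected does not change. The price is information: in affected patients, later assessments of the remaining lesions leave the main display, and some best changes will look less favourable. A patient whose T-NI lesion is injected before the first on-treatment assessment would have no value in the main display and should be listed as such.

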#### 7.7 EXTENT OF EXPOSURE

Duration of treatment with BI 1387446 and Duration of treatment with ezabenlimab will be summarized descriptively.

The Cumulative total dose for both trial drugs and the Number of cycles initiated will also be summarized.

The Number of patients with at least one dose reduction of BI 1387446 will be displayed.

#### 7.8 SAFETY ANALYSIS

All safety analyses will be performed on the treated set, besides the analyses for MTD determination. These will be performed on the MTD set. Treated patients will be analyzed separately for each treatment arm and according to their initial planned treatment.

Patients who cross over from Arm A to Arm B will be considered for both treatment arms: in Arm A according to their initial planned treatment and in Arm B according to their planned combination treatment at cross-over to Arm B. See Section 6.1 for details.

Safety data recorded during the Residual Effect Period (REP) of 90 days will be considered as on-treatment.

#### 7.8.1 Adverse Events

Date: 8 Apr 2024, Version 1.0

The analyses of AEs will be descriptive in nature. All analyses of AEs will be based on the number of subjects with AEs and NOT on the number of AEs. The analysis will be based on BI standards (9.6). AEs will be coded using the most recent version of MedDRA. The severity of AEs will be scaled according to the Common terminology Criteria for Adverse Events (CTCAE) version 5.0.

The analysis of AEs will be based on the concept of treatment emergent AEs. That means that all AEs occurring between first administration of trial medication until 90 days after last administration of trial medication will be considered treatment-emergent and assigned to the initial planned treatment.

All AEs occurring before first administration of trial medication will be assigned to 'screening' and all AEs occurring after last administration of trial medication + 90 days will be assigned to 'follow-up' (for listings only). For details on the treatment definition, see Section 6.1.

AEs will be reported with start day and end day as calculated from the first day of treatment with trial medication. For listings displaying AEs during the screening or follow-up period, the start and stop day are calculated from the start of the respective analysis period.

Proprietary confidential information © 2024 Boehringer Ingelheim International GmbH or one or more of its affiliated companies.

An overall summary of AEs will be presented.

AEs will be displayed by the initial planned dose of trial medication administered on the first day of treatment. Patients who undergo a cross-over from Arm A to Arm B during the trial will be displayed in both treatment arms: by the initial planned dose of study medication in Arm A and by the planned combination dose in Arm B.

The frequency of patients with AEs during the on-treatment period will be summarized by treatment, primary system organ class (SOC) and preferred term (PT) for each of the following AE tables:

The frequency of patients with AEs during the on-treatment period will be summarized by treatment, primary system organ class (SOC) and preferred term (PT) for each of the following AE tables:

- DLTs
- All AEs by highest CTCAE grade
- Serious AEs by highest CTCAE grade
- Investigator assessed BI 1387446 related AEs by highest CTCAE grade
- Investigator assessed ezabenlimab related AEs by highest CTCAE grade
- Investigator assessed BI 1387446 related SAEs by highest CTCAE grade
- Investigator assessed ezabenlimab related SAEs by highest CTCAE grade
- Investigator assessed Adverse Events of Special Interest (AESI) by highest CTCAE grade
- Investigator assessed infusion-related AEs by highest CTCAE grade
- Investigator assessed immune-related AEs by highest CTCAE grade
- Investigator assessed procedural complication (biopsy/injection) AEs by highest CTCAE grade
- AEs leading to treatment discontinuation of BI 1387446 by highest CTCAE grade
- AEs leading to treatment discontinuation of ezabenlimab by highest CTCAE grade
- AEs leading to dose reduction of BI 1387446 by highest CTCAE grade
- AEs leading to death

The SOC will be sorted alphabetically, preferred terms will be sorted by frequency (within SOC).

Listings of DLTs, fatal AEs, serious AEs, AEs leading to treatment discontinuation of BI 1387446, AEs leading to treatment discontinuation of ezabenlimab and AEs leading to dose reduction of BI 1387446 will be provided.

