5.2.7.2 Adverse event collection and reporting

5.2.7.2.1 AE Collection

The Investigator shall maintain and keep detailed records of all AEs in the patient files.

The following must be collected and documented on the appropriate CRF(s) by the Investigator:

- From signing the informed consent onwards until the individual patient's end of trial: all AEs (serious and non-serious) and all AESIs.
- After the individual patient's end of trial:
the Investigator does not need to actively monitor the patient for new AEs but should only report any occurrence of cancer and trial treatment related SAEs and trial treatment related AESIs of which the Investigator may become aware of by any means of communication, e.g. phone call. Those AEs should be reported on the BI SAE form (see [Section 5.2.7.2.2](#)), but not on the CRF.

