7.2.5 Safety analyses

Adverse events will be coded using the Medical Dictionary for Drug Regulatory Activities (MedDRA). Standard BI summary tables and listings will be produced. All adverse events with an onset between start of treatment and 90 days after the last dose of trial medication will be assigned to the on-treatment period for evaluation.

All treated patients will be included in the safety analysis. In general, safety analyses will be descriptive in nature and will be based on BI standards. No hypothesis testing is planned.

Statistical analysis and reporting of adverse events will concentrate on treatment-emergent adverse events, i.e. all adverse events occurring between start of treatment and 90 days after the last dose of trial medication. Adverse events that start before first drug intake and deteriorate under treatment will also be considered as 'treatment-emergent'.

Frequency, severity, and causal relationship of adverse events will be tabulated by system organ class and preferred term after coding according to the current version of the Medical Dictionary for Drug Regulatory Activities (MedDRA) at database lock.

Laboratory data will be analysed both quantitatively as well as qualitatively. The latter will be done via comparison of laboratory data to their reference ranges and via assessment of CTCAE grades. Values defined as clinically relevant will be summarised. Treatment groups will be compared descriptively with regard to distribution parameters as well as with regard to frequency and percentage of patients with abnormal values or clinically relevant abnormal values.

Vital signs, physical examinations, or other safety-relevant data observed at screening, baseline, during the course of the trial and at the end-of-trial evaluation will be assessed with regard to possible changes compared to findings before start of treatment.

Other safety analyses (AESIs, centrally evaluated ECG, etc.) will be specified in detail in the TSAP.

[REDACTED]

[REDACTED]

[REDACTED]

[REDACTED]

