## 6. GENERAL ANALYSIS DEFINITIONS

## 6.1 TREATMENT(S)

In this Phase I trial treatments are not randomized. In Arm A and Arm B, different dose levels of BI 1387446 alone (Arm A) or of BI 1387446 in combination with 240 mg of ezabenlimab (Arm B) are being administered.

If not specified otherwise, all analyses will be performed for each treatment arm separately. Data will be presented by initial treatment, i.e. within each treatment arm for all dose cohorts separately and in total over all dose cohorts of that arm.

For safety summaries, events that start from the first administration of any trial medication until 90 days after the last administration of any trial medication (residual effect period, REP) will be assigned to the on-treatment period for evaluation. If not specified otherwise, all safety tables will be based on the on-treatment period. Adverse events that have an onset during the screening or the follow-up period will be displayed in separate listings from those that occurred during the on-treatment period.

The MTD evaluation period will be derived as the time from the first administration of study drug to the start of the second treatment cycle, i.e., in more detail as the time from the first administration of (any) trial medication to the start of the 2nd administration of ezabenlimab or 4th administration of BI 1387446 (whatever from the latter two comes first). In the case that the 2nd administration of ezabenlimab and/or the 4th administration of BI 1387446 are not given, the MTD evaluation period ends 90 days after the last administration.

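### SAP 6.1 and 7.8.1 omit the protocol's rule that an AE starting before first dose and worsening on treatment is treatment-emergent

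*SAP*

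**What the plan says.** **Protocol 7.2.5 (Safety analyses).** AE reporting is to concentrate on treatment-emergent events. These are "all adverse events occurring between start of treatment and 90 days after the last dose of trial medication". The section then widens the definition: "Adverse events that start before first drug intake and deteriorate under treatment will also be considered as" treatment-emergent.

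**SAP 6.1 (Treatments).** The on-treatment period for safety summaries takes in "events that start from the first administration of any trial medication until 90 days after the last administration of any trial medication". Assignment goes by onset: "Adverse events that have an onset during the screening or the follow-up period will be displayed in separate listings".

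**SAP 7.8.1 (Adverse Events).** AEs "between first administration of trial medication until 90 days after last administration of trial medication will be considered treatment-emergent". No deterioration clause follows. Instead, "All AEs occurring before first administration of trial medication will be assigned to" screening, a category that the same paragraph reserves for listings. The tables are restricted accordingly: "The frequency of patients with AEs during the on-treatment period will be summarized".

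**Protocol 5.2.7.2.1 (AE Collection).** From consent onwards the investigator records "all AEs (serious and non-serious) and all AESIs". AEs with onset before the first dose will therefore be in the database, and the SAP plans a listing for them.

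**The concern.** The protocol and the SAP give different definitions of the set of events on which the safety tables rest. The SAP introduction says that it builds on Section 7 of the protocol. The readable part of SAP Section 4, where changes to the planned analysis belong, deals with further endpoints dropped after development was terminated and is silent on this definition. As written, this is an undeclared departure.

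Characterising safety is a main objective of this first-in-human trial. Dose cohorts are small, with an intended maximum of 8 patients per dose level and arm, so one missing event can change how a cohort's table reads. Pre-dose events are also plausible here. Baseline biopsies of the projected injection lesion and of a non-injected lesion are mandatory before the first injection (Flow Chart, footnotes 21 and 28), and SAP 7.8.1 plans a table of biopsy and injection complications. A biopsy complication that starts before dosing and worsens after injection into the same lesion is the type of event that could be lost from that table.

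**Working it through.** No figure is involved, so the check compares the rules and follows particular events through them.

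**Rules side by side**

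| Element | Protocol 7.2.5 | SAP 6.1 and 7.8.1 |
|---|---|---|
| Onset from first dose to last dose + 90 days | Treatment-emergent | Treatment-emergent |
| Onset before first dose, no worsening | Not treatment-emergent | Screening listing |
| Onset before first dose, worsens under treatment | Treatment-emergent | Screening listing, no exception stated |

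The two differ in the third row only. Protocol 7.2.5 also assigns events to its on-treatment period by onset, but it then bases reporting on the wider treatment-emergent set. The SAP gives both terms the same onset window.

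**Events traced through the rules**

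1. *Condition already present before trial inclusion.* Protocol 5.2.7.1.1 treats pre-existing abnormalities as baseline conditions and requires worsening of a pre-existing condition to be recorded as an AE. On-treatment worsening then gives an AE with on-treatment onset. It is tabulated under both documents.
2. *Laboratory worsening.* SAP 7.8.2 tabulates shifts from baseline to worst CTCAE grade, and values of grade 2 or higher that have risen at least one grade from baseline. This does not depend on AE onset dates, so the laboratory change is shown in either case.
3. *AE with onset between consent and first dose, worsening entered as a new record.* The new record has an on-treatment onset. It is tabulated under both documents.
4. *The same AE kept as one record, for example Grade 1 before dosing and Grade 3 after.* Under the protocol it is treatment-emergent. Under the SAP it is a screening AE. It appears in a listing and is missing from the on-treatment tables, including the table of all AEs by highest CTCAE grade.

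The conflict has a practical effect in case 4. Neither document says whether an AE already open in screening gets a new record when it worsens, so case 4 is neither confirmed nor ruled out.

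**Direction and size.** For events starting before first dose, the SAP's set is contained in the protocol's set, so following the SAP can only lower the treatment-emergent counts and grades. The documents give no rate of pre-dose AEs, no rate of worsening and no number of patients treated, so the amount cannot be calculated.

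**The case against.** The strongest reply is that this is a sentence left out and not a change of rule. The SAP says that it follows Section 7 of the protocol, and it cites a sponsor standard for AE analysis (SAP reference 9.6) that may deal with worsening. Most patients with symptoms or laboratory abnormalities at entry are covered by the baseline-condition and laboratory rules in cases 1 and 2. Events sent to screening still appear in a listing.

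Much of this stands, and it narrows the exposed group to case 4. It does not remove the conflict. The content of the standard is not in the documents, and a general reference to the protocol does not override an explicit SAP rule that covers all pre-dose AEs without exception.

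A reader might infer three stronger points, which the documents do not support:

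- *That worsening of any symptom or abnormality present at entry is lost.* Protocol 5.2.7.1.1 and SAP 7.8.2 speak against this.
- *That the same contradiction arises at cross-over.* The protocol's clause concerns events before first drug intake. An AE that begins in Arm A starts after first intake, so no protocol rule is broken. Such an AE also stays in the Arm A on-treatment tables. The open question is to which arm the worsening belongs, and the present rule could raise Arm A's worst grades, so the one-sided direction does not hold there.
- *That a patient count can be given.* Assuming that 5% to 20% of the planned 78 patients are affected would give 0.05 × 78 = 3.9 to 0.20 × 78 = 15.6, or about 4 to 16. Those percentages have no source in the documents and are not limited to case 4, and 78 is planned enrolment in a programme since terminated.

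**Conclusion.** The SAP's definition is wrong as written because it contradicts protocol 7.2.5 and declares no change. The consequence is limited to AEs that start between consent and first dose, worsen on treatment and are held as one record. Those events would be missing from the on-treatment tables and appear only in a listing. How many there are cannot be determined from the documents. The conclusion assumes that the unseen sponsor standard does not override the SAP's explicit wording and that no redacted part of SAP Section 4 announces the change. The text mismatch is certain, but its practical effect depends on a recording convention that is not stated. The outputs concerned are descriptive safety tables, and no effect on the dose-toxicity model or the MTD is shown. It should be corrected because the remedy is short and returns the SAP to the protocol's definition.

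**What to change.** In SAP 6.1 and 7.8.1:

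1. Restore the protocol's clause, so that an AE starting before the first dose and deteriorating during the on-treatment period counts as treatment-emergent and enters the tables.
2. State how deterioration is identified: either a new AE record with an on-treatment onset, or a grade increase recorded within the existing record. A CTCAE grade increase is a narrower test than the protocol's term, so the choice should be explicit.
3. State that the event is tabulated at its highest on-treatment grade where this is recorded. Neither document says that dated grade changes within one AE record are collected, so this should be checked against the eCRF first.

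If the onset-only rule is intended, declare it in SAP Section 4 with the reason.

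As a suggestion only, add a sentence on how an AE that starts in Arm A and worsens after the first Arm B dose is attributed between the arms.

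The cost is a few sentences and a small programming change, provided the grade data exist. Reported AE frequencies may rise slightly.
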